4.1.3 Selection of doses in the trial

4.1.3.1 Initial dose and dose levels to be evaluated

Dose cohorts of BI 836845 to be evaluated are indicated in [Table 4.1.3.1: 1](#). Actual number of evaluable patients to be entered will depend on the incidence of DLTs. To identify the MTD, 6 patients must enter the dose cohort. Dose escalation will proceed as outlined in [Section 4.1.3.4](#) until the MTD or 1400 mg dose cohort has been reached. Additional 6 patients may also be entered as an expansion cohort to be recommended a relevant biological dose.

Table 4.1.3.1: 1

Dose cohorts and number of evaluable patients to be enrolled

Dose cohort	Number of evaluable patients
750 mg	3 to 6
1000 mg	3 to 6
1400 mg	6

As shown in [Section 1.4](#), patients' tolerability was ensured until 1800 mg (qw schedule) and 3600 mg (q3w schedule) in 1280.1 and 1280.2 trials, respectively. Reported drug-related adverse events were mainly predictable and manageable. The rationale behind the starting dose of 750 mg is based on safety and efficacy results of 1280.1 and 1280.2 trials. Such a sufficient tolerability will be expected at 750 mg of BI 836845 in Japanese patients with advanced solid tumours. In addition, objective tumour response as PR was observed in Taiwanese patients who were treated in the close vicinity of the starting dose, 800 mg (see Section 1.4 for details).

After confirmation of sufficient tolerability in patients who are treated at 750 mg of BI 836845, the 1000 mg dose cohort will be opened. The dose of 1000 mg is an identified relevant biological dose which estimated to neutralise more than 90% for free IGF-1 and 64% for free IGF-2 in the blood from PK-PD modelling results. The 1400 mg dose cohort is also planned as a maximum dose because additional neutralisation of more than 2% for free IGF-1 and more than 7% for free IGF-2 are estimated at 1400 mg, and no effective neutralisation of free IGF-1 and free IGF-2 is expected more than 1400 mg.

4.1.3.2 Dose-limiting toxicities

For definition of a DLT, it is essential that patients are treated sufficiently according to supportive care standards, and baseline conditions, coexisting symptoms, and/or transient laboratory abnormalities of patients are also considered. A drug-related adverse event constitutes a DLT, if one of the following applies during Cycle 1:

Haematological toxicities:

- CTCAE grade 4 neutropenia (neutrophil counts of $<500/\mu\text{L}$) lasting 7 or more days
- Febrile neutropenia (neutrophil counts of $<1000/\mu\text{L}$ with once observed a temperature of $\geq38.3^\circ\text{C}$ or a sustained temperature of $\geq38.0^\circ\text{C}$ for more than 1 hour)
- Infection with neutrophil counts of $<1000/\mu\text{L}$
- CTCAE grade 4 thrombocytopenia (platelet counts of $<25\,000/\mu\text{L}$) or CTCAE grade 3 thrombocytopenia (platelet counts of $<50\,000\text{--}25\,000/\mu\text{L}$) associated with bleeding requiring platelet transfusion

Non-haematological toxicities:

- CTCAE grade 3 or 4 non-haematologic toxicity (except incompletely treated nausea, untreated vomiting, untreated diarrhoea, skin toxicity, fatigue, infusion reaction, electrolyte, hyperglycaemia, AST, or ALT). The following drug-related non-haematological toxicities should be defined as DLTs:
 - CTCAE grade ≥ 2 infusion reaction despite adequate pre-medication
 - CTCAE grade ≥ 2 nausea and/or vomiting persisting for 7 or more days despite antiemetic treatment
 - CTCAE grade ≥ 3 skin toxicity despite adequate supportive care measures for up to 14 days if it does not reach an improvement to grade ≤ 2
 - CTCAE grade ≥ 3 hyperglycaemia resistant to treatment with anti-diabetic agents
 - Any electrolyte CTCAE grade 3 adverse event which is refractory to optimal correction therapy
 - No recovery from a non-DLT CTCAE grade ≥ 3 toxicity to grade ≤ 1 within 14 days of administered dose
 - Sustained CTCAE grade 3 fatigue or asthenia for longer than 96 hours associated with deterioration of ECOG performance status

It is understood that also other drug-related adverse events (CTCAE grade 2) may carry the potential to be significant enough to necessitate treatment interruption or discontinuation, and as such qualify as DLT. Such adverse events will be required the confirmation after thorough discussion between the investigator and the sponsor on a case-by-case basis.

All adverse events which are determined as DLTs occurring during Cycle 2 or later (DLT-equivalent adverse events) will also be considered during evaluation of the overall safety in the trial.

All DLTs and DLT-equivalent adverse events have to immediately be reported to the sponsor. DLTs and DLT-equivalent adverse events must be determined after discussion and agreement with the investigator and the sponsor. The sponsor may ask for the opinion of the assigned external expert if needed.

[figure not shown]

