An external expert who is independent of the study sites (investigators) and the sponsor, with expertise in oncology clinical trials, will be assigned. The reviews by the assigned external expert ensure the adequacy of DLT evaluation and/or dose escalation which discussed and agreed between the study site (investigators) and the sponsor as an independent third party. In addition, an external expert can make recommendations to the sponsor regarding study continuation, amendment, or discontinuation as necessary when it is brought important safety information about the trial and/or investigational drug.

Details on handling of the trial supplies including responsible institutions are given in [Sections 4.1.6, 4.1.7, and 4.1.8](#) of this CTP.

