4.2.1.1 Management and grading of infusion reactions

The investigational drug infusions should always be administered in a hospital environment and under close supervision of the medically qualified staff member with immediate availability of full resuscitation facilities.

Infusion reactions may occur during infusion with BI 836845 and include pyrexia, chills, rigors, dyspnoea, urticaria, bronchospasm, hypotension, and hypertension. **A 1-hour observation period is recommended following each infusion.** Mild to moderate infusion reactions may be managed with a slower infusion rate and prophylactic antihistamines for subsequent dosing. Severe reactions require immediate interruption of infusion. The details are summarised in Table 4.2.1.1: 1. The grading of hypersensitivity reactions will be according to CTCAE version 4.03.

Table 4.2.1.1: 1 Infusion reaction management

Intensity for infusion reaction	Management
CTCAE grade 1 or 2	In the event of a mild to moderate CTCAE grade 1 or 2 non-allergic infusion reaction, the infusion rate should be reduced by 50%. Once the adverse event has resolved, the investigator should wait and deliver the infusion at the reduced rate for another 30 minutes. If tolerated, the infusion rate may then be increased to the next close rate on the patient's infusion schedule. In case of a CTCAE grade 2 adverse event that requires therapy (e.g. antihistamines, nonsteroidal anti-inflammatory drugs [NSAIDs], steroids, narcotics, intravenous fluids) or infusion interruption and resolves promptly the infusion may also be restarted at half of the infusion rate at the time of onset of the infusion reaction.
CTCAE grade 3	For Patients experiencing CTCAE grade 3 infusion reaction, infusion should be interrupted immediately and patients should receive aggressive symptomatic treatment. Only after all the symptoms have disappeared the infusion should be started. The infusion rate at restart should be half of the infusion rate at the time of onset of the infusion reaction.
CTCAE grade 4	For patients experiencing CTCAE grade 4 infusion reaction such as anaphylaxis during an infusion should have infusion immediately stopped and receive appropriate treatment including use of resuscitation medications and/or equipment that must be available. Such patients should be discontinued the study treatment and should be followed up.

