4.2.2 Restrictions

4.2.2.1 Restrictions regarding concomitant treatment

The use of concomitant drugs for prophylactic purpose is prohibited to prevent the expression of drug-related adverse events. Additional experimental anti-cancer treatment and/or standard chemotherapy, immunotherapy, hormone treatment, with the exception of megestrol acetate and LHRH analogues, is not allowed during the trial.

For symptom control palliative radiotherapy may be permitted after discussion and agreement with the investigator and the sponsor on a case-by-case basis (e.g. for bone metastases). The impact of any palliative radiotherapy on tumour assessments must be documented.

Any concomitant medication should be reduced to the clinically necessary minimum on the days of BI 836845 infusion.

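### A grade 4 infusion reaction without pre-medication in Cycle 1 ends treatment but meets no written DLT criterion, so it can drop out of the MTD count

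*Protocol*

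**What the plan says.** The general non-haematological rule in Protocol Section 4.1.3.2 makes drug-related grade 3 or 4 toxicity in Cycle 1 a DLT, with a list of exceptions: "except incompletely treated nausea, untreated vomiting, untreated diarrhoea, skin toxicity, fatigue, infusion reaction, electrolyte, hyperglycaemia, AST, or ALT". Infusion reaction is on that list with no upper grade limit. It returns as a DLT in its own bullet: "CTCAE grade ≥ 2 infusion reaction despite adequate pre-medication".

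Two other provisions of that section could apply. One makes a grade 3 or higher toxicity that was not already a DLT into one if it has not come down to grade 1 or below within 14 days of dosing. The other allows discretion beyond the list: "It is understood that also other drug-related adverse events (CTCAE grade 2) may carry the potential to be significant enough". DLT status is settled jointly: "DLTs and DLT-equivalent adverse events must be determined after discussion and agreement with the investigator and the sponsor". Section 3.1.1 adds an independent expert: "The reviews by the assigned external expert ensure the adequacy of DLT evaluation and/or dose escalation".

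On pre-medication, Section 4.2.2.1 states: "The use of concomitant drugs for prophylactic purpose is prohibited to prevent the expression of drug-related adverse events". Section 4.2.1.1 relaxes this after a mild to moderate reaction, allowing "prophylactic antihistamines for subsequent dosing". For grade 4, Table 4.2.1.1: 1 is explicit: "Such patients should be discontinued the study treatment and should be followed up".

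Section 3.3.5 lists stopping in Cycle 1 for a non-DLT reason as a ground for replacement, decided case by case by the investigator and sponsor. SAP Sections 6.3 and 7.4 exclude replaced patients from the MTD determination.

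**The concern.** Each rule is reasonable alone, but together they leave a gap at the severe end. The infusion-reaction bullet requires pre-medication to have been given, and the protocol does not allow it until a milder reaction has occurred. A patient whose first reaction is grade 4 never reaches a pre-medicated infusion, because treatment stops. The test that would restore the event as a DLT cannot be met.

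The result inverts severity. A grade 2 reaction under pre-medication is a DLT, and another grade 2 event that forces a stop may be declared one. A life-threatening reaction that the protocol itself says must end treatment is not on the list.

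The primary endpoint is the MTD, identified by the number of patients with DLTs, and Section 4.1.3.4 bases escalation on reported DLTs. An uncounted event would therefore affect the dose given to the next patients as well as the final table. Infusion reaction is a risk that Section 2.3 names.

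**Working it through.** **The plan's own figures.** Three dose cohorts of up to six give 3 × 6 = 18 evaluable patients (Sections 3.3 and 7.6). Adding the expansion cohort gives 18 + 6 = 24, the synopsis maximum. Both reproduce. The decision rule (Section 4.1.3.3) is at most one patient with a DLT among six evaluable.

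**The criteria applied in turn.** Take a drug-related grade 4 infusion reaction at a Cycle 1 infusion without pre-medication, recovering to grade 1 or below within 14 days.

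| Provision | Met? | Reason |
|---|---|---|
| General grade 3 or 4 rule (4.1.3.2) | No | Infusion reaction is excepted at any grade |
| Infusion-reaction bullet (4.1.3.2) | No | No pre-medication was given, and no later infusion follows (4.2.1.1) |
| 14-day non-recovery bullet (4.1.3.2) | No | The reaction recovered in time |
| Discretion beyond the list (4.1.3.2) | No | It names grade 2 |

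The patient has then stopped in Cycle 1 for a reason other than a DLT. If replaced, the patient leaves the MTD set. If kept, the patient is one of the six without a DLT. Either way the event adds 0 to the count.

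**Illustration.** Assume two such reactions at 1400 mg, both patients replaced, and no other DLT. The count is 0/6, and 1400 mg is deemed sufficiently tolerated. Counted as DLTs, the result is 2/6, which fails the rule.

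**How often this could matter.** The documents give no rate for Japanese patients, so the per-patient rate p is an assumption. If such reactions were counted, the chance that they alone fail a six-patient cohort is

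P(≥2 of 6) = 1 − (1−p)⁶ − 6p(1−p)⁵

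If every such patient were replaced, the expected number of replacements needed to reach six evaluable is 6p/(1−p).

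| Assumed p | P(≥2 of 6) | Expected replacements |
|---|---|---|
| 0.02 | 0.0057 | 0.12 |
| 0.05 | 0.0328 | 0.32 |
| 0.0605 | 0.0466 | 0.39 |

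**Where 0.0605 comes from.** Section 1.4 says that trial 1280.1 had one drug-related severe event, a pulmonary haemorrhage, which implies no drug-related severe infusion reaction. Its patient number is taken as 48, the denominator given there for stable disease; 48 + 33 (trial 1280.2) = 81, the stated number treated. The one-sided 95% upper bound from 0/48 is 1 − 0.05^(1/48) = 0.0605. Using it here assumes the same rate across doses, populations and pre-medication practice. It covers all severe infusion reactions, so grade 4 alone should be rarer.

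**The case against.** The strongest counter-argument concerns the discretion clause. It reaches down to grade 2 because such an event may force interruption or discontinuation. A grade 4 reaction that must end treatment fits that reason better than any grade 2 event, so declaring it a DLT would follow the logic of the clause. There are also several safeguards: joint determination of DLTs, an independent expert, case-by-case replacement, and confirmation of exclusions at the report planning meeting. The event remains visible too, because SAEs are reported immediately and SAP Section 7.8 puts all treated patients in the safety tables.

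Most of this stands as a limit on consequences. Sensible people would probably call the event a DLT, and it would not be hidden. But the clause as written names grade 2, and none of the safeguards supplies a criterion. The right count would depend on going beyond the list.

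A second argument is that the exception is deliberate: several toxicities count only when they persist despite supportive care. That explains sparing a transient grade 2 or 3 reaction, after which the infusion can restart at half rate. It does not explain sparing a grade 4 reaction, after which treatment may not continue.

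The remaining points are rarity and timing. Both are fair. At an assumed 1% the formula above gives about 0.15%. The current protocol version also records the decision to end oncology development of the drug, so a rewording now is unlikely to alter dosing. Neither changes what the criterion says.

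**Conclusion.** The concern holds. Under the written criteria, a grade 4 infusion reaction without pre-medication in Cycle 1 that recovers to grade 1 or below within 14 days is not a DLT, although it ends treatment. The patient may be replaced and left out of the MTD count, or kept as a patient without a DLT.

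The probability is low, but the affected quantity is the primary endpoint. At assumed rates from 2% to 6.1%, counting these reactions would by itself fail a six-patient cohort about 0.6% to 4.7% of the time, and the upper figure is likely too high for grade 4 alone. The conclusion rests on reading the DLT list as written. Replacement is possible, not automatic, and the investigator and sponsor could agree on a different call. The point should be fixed because the correction is small and specific.

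**What to change.** In Protocol Section 4.1.3.2, split the infusion-reaction bullet in two:

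- CTCAE grade 4 or higher infusion reaction, with or without pre-medication.
- CTCAE grade 2 or 3 infusion reaction, keeping the existing pre-medication condition.

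Grade 5 stays covered. A patient with a grade 4 reaction then has a DLT, so stopping treatment for it is no longer a ground for replacement under Section 3.3.5, and the SAP needs no change.

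Optionally, add grade 4 infusion reaction to the discontinuation criteria in Section 3.3.4.1. Section 4.1.3.6 resumes treatment at a lower dose after a DLT unless a Section 3.3.4 criterion is met. The general undue-toxicity criterion arguably covers this already, but naming the event removes any conflict with Table 4.2.1.1: 1.

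The cost is one wording edit and one optional line, with no added procedures. The downside is that a cohort may expand, stop or de-escalate earlier if such a reaction occurs.

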The potential risks associated with BI 836845 are unknown in Japanese patients and unexpected or infrequent adverse events may occur in the clinical trial. The proposed trial will evaluate stepwise dose escalation of BI 836845, and the investigator should carefully be monitored the patients' safety during trial participation.

Although BI 836845 is a fully human antibody given intravenously, there may be potential for infusion reactions (e.g. infusion-related reactions, injection site reactions, immune system disorders) to occur. Such infusion reactions will be graded thoroughly and appropriate preventative and/or corrective actions implemented following the standard of care for such adverse events.

Although rare, a potential for drug-induced liver injury (DILI) is under constant surveillance by sponsors and regulators. Therefore, this study requires timely detection, evaluation, and follow-up of laboratory alterations of selected liver laboratory parameters to ensure patients' safety.

Together with the encouraging preliminary signs of anti-tumour activity observed (see Section 1.4 for details), this 1280.15 trial had warranted, until the negative efficacy results for BI 836845 in the placebo-controlled randomised Phase II 1280-0022 trial, continuation of clinical investigation of BI 836845 in patients with solid tumours. The 1280-0022 Phase II placebo-controlled, randomised trial recently completed primary endpoint analysis and showed no added benefit of BI 836845 compared to placebo, in patients with everolimus and exemestane backbone therapy, when treating trial participants with metastatic breast cancer, HR+, HER2- and non-visceral disease. No new safety signals were observed with the addition of BI 836845 to the everolimus and exemestane combination.

In consideration of these topline results of 1280-0022, as of 19 October, 2021, Boehringer Ingelheim recommended to immediately discontinue all BI 836845 treatments. As a consequence of the worsening in benefit-risk for BI 836845, Boehringer Ingelheim also

Proprietary confidential information © 2024 Boehringer Ingelheim International GmbH or one or more of its affiliated companies

decided to terminate all oncology drug development for BI 836845 including the cessation of further manufacturing of investigational medicinal product BI 836845.

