4.1.4 Drug assignment and administration of doses for each patient

A method of drug assignment for patients is described in [Section 4.1.2](#).

BI 836845 will be administered intravenously over 1 hour with repeated administration weekly until patients meet any of criteria for discontinuation (see [Section 3.3.4](#) for definition) as per the Flow Chart. Infusion duration on Day 1 of Cycle 1 may be extended to over 1 hour and up to a maximum of 3 hours in cases of CTCAE grade ≥ 2 infusion reactions (see [Section 4.2.1.1](#) for grading and management of infusion reactions). **An infusion duration of less than 1 hour must be avoided because mannitol is used in the formulation of BI 836845.**

Patients will be treated at the assigned dose during the study treatment unless patients are required the dose reduction (see Section 4.1.3.6 for definition). Intra-patient dose escalation will not be allowed.

In case of a delay of infusion, the reason and the exact time of deviation must be recorded in the eCRF because the accuracy of this information is crucial for the proper evaluation and appraisal of pharmacokinetics and other data. In case of a drug interruption, the reason must be recorded in the eCRF. Administration status is not recorded in the eCRF during the rollover part.

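### As worded, a grade 3-4 infusion reaction at a Cycle 1 infusion given without pre-medication, and recovered within 14 days, meets no listed DLT criterion; a grade 4 case may also leave the MTD set.

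*Protocol*

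**What the plan says.** **DLT definition (Protocol 4.1.3.2).** A drug-related grade 3 or 4 non-haematological toxicity in Cycle 1 is a DLT, but infusion reaction is on the list of exceptions, without qualification. It returns as a DLT when it is a grade 2 or higher "infusion reaction despite adequate pre-medication". Another criterion covers a non-DLT toxicity of grade 3 or higher that has not recovered to grade 1 or less within 14 days. A case-by-case clause follows: "It is understood that also other drug-related adverse events (CTCAE grade 2) may carry the potential" to qualify.

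**Who decides (Protocol 4.1.3.2 and 3.1.1).** "DLTs and DLT-equivalent adverse events must be determined after discussion and agreement with the investigator and the sponsor". An external expert reviews DLT evaluation.

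**Pre-medication.** Protocol 4.2.2.1: "The use of concomitant drugs for prophylactic purpose is prohibited to prevent the expression of drug-related adverse events". Protocol 4.2.1.1 says that mild to moderate reactions may be managed with a slower rate and "prophylactic antihistamines for subsequent dosing". Protocol 2.3 foresees "appropriate preventative and/or corrective actions implemented following the standard of care for such adverse events".

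**First infusion (Protocol 4.1.4).** "Infusion duration on Day 1 of Cycle 1 may be extended to over 1 hour and up to a maximum of 3 hours". The trigger is a reaction of grade 2 or higher, so such reactions are foreseen at the first dose.

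**After a grade 4 reaction.** Table 4.2.1.1: 1 has the patient stop study treatment. Protocol 3.3.5 lists a Cycle 1 discontinuation for a reason other than DLT as grounds for replacement, decided case by case. SAP 6.3 and 7.4 exclude replaced patients from the MTD determination.

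**MTD (Protocol 4.1.3.3, SAP 5.1).** The highest dose with a DLT in no more than 1 of 6 patients. SAP 7.4 takes the DLT definition from Protocol 4.1.3.2 and adds no criterion.

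**The concern.** The MTD rule uses only the DLT count. For infusion reactions, that count turns on whether the patient had been pre-medicated, while another section prohibits prophylaxis and states no exception. A serious reaction at a first infusion can therefore fall outside every listed criterion.

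The grade 4 case is the sharpest. The patient stops. If the event is not called a DLT, the stop is a reason for replacement, and a replaced patient leaves both the numerator and the denominator of the primary endpoint. At stake is whether a cohort's count out of 6 reflects a severe reaction to the study drug. No planned summary in the visible SAP shows what that count would be with such reactions included.

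**Working it through.** **1. The plan's own figure.** Three cohorts of up to 6 give 3 × 6 = 18 evaluable patients, and 18 + 6 in the expansion cohort = 24. Both agree with the protocol (7.6 and synopsis).

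**2. Each listed criterion against the case.** The case is a drug-related grade 3 or 4 infusion reaction in Cycle 1, at an infusion given without pre-medication, recovered to grade 1 or less within 14 days.

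| Criterion in Protocol 4.1.3.2 | Met? |
|---|---|
| Four haematological criteria | No, different toxicities |
| General grade 3-4 non-haematological rule | No, infusion reaction excepted |
| Grade 2 or higher infusion reaction despite pre-medication | No, none given |
| Nausea/vomiting, skin, hyperglycaemia, electrolyte, fatigue criteria | No, different toxicities |
| No recovery within 14 days | No, recovered |
| Case-by-case clause | No, names grade 2 only |

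No listed criterion is met.

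**3. Can the case arise?** Yes. Prophylaxis is prohibited (4.2.2.1), and antihistamines are mentioned only for later doses (4.2.1.1). An infusion without pre-medication is thus the expected state, at least for the first dose.

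**4. Size.** The documents give no infusion reaction rate, so the rates below are assumptions.

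- Reaction rate r: 1%, 2%, and an upper bound from trial 1280.1. Protocol 1.4 reports one drug-related severe event there, a pulmonary haemorrhage, and gives 48 patients. Reading this as 0/48 severe infusion reactions, the one-sided 95% upper bound is 1 − 0.05^(1/48) = 0.0605, or 6.1%.
- Other-DLT rate q: 1/48 = 0.0208, from the one DLT that Protocol 1.4 describes in that trial. Reactions and other DLTs are taken as independent.
- Pass probability: P(X ≤ 1) = (1 − p)^6 + 6p(1 − p)^5.
- Counted: p = 1 − (1 − r)(1 − q).
- Not counted, patient kept as a non-event: p = q, so P = 0.9938 at every r.
- Not counted, patient replaced: p = q / [q + (1 − r)(1 − q)].

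| r | p counted | P counted | p replaced | P replaced | At least one reaction in 6: 1 − (1 − r)^6 |
|---|---|---|---|---|---|
| 0.01 | 0.0306 | 0.987 | 0.0210 | 0.9937 | 0.059 |
| 0.02 | 0.0404 | 0.978 | 0.0212 | 0.9936 | 0.114 |
| 0.0605 | 0.0801 | 0.923 | 0.0221 | 0.9931 | 0.312 |

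Against a patient kept as a non-event, the differences are 0.9938 − 0.9870 = 0.007, 0.9938 − 0.9780 = 0.016 and 0.9938 − 0.9226 = 0.071.

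**The case against.** **The exception looks deliberate, and the passages can be read in sequence.** Other excepted toxicities also return only when supportive treatment fails. On this reading there is no prophylaxis at first, antihistamines follow a mild to moderate reaction, and a recurrence despite them is a DLT. The preventive actions in Protocol 2.3 fit that order. This stands, and it rules out the claim that the sections flatly contradict each other. It does not reach a grade 4 reaction at an infusion without pre-medication: that patient stops, so there is no later dose at which the criterion could apply. For grade 3, antihistamines are mentioned only after mild to moderate reactions.

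**Agreement and expert review are safeguards.** They are: nothing bars the investigator and sponsor from calling the event a DLT, and replacement is not automatic. But these are processes. The one written extension names grade 2.

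**The event is reported anyway.** This stands. Cycle 1 adverse events are presented separately (Protocol 7.3.3), and the treated-set tables cover drug-related events by grade and events leading to discontinuation (SAP 7.8, 7.8.1). A reader might infer that the reaction vanishes from the report; it does not. What can miss it is the DLT count.

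**Recorded term.** A reader might infer that DLT status depends on the term recorded, because hypotension or bronchospasm entered alone would fall under the general grade 3-4 rule. Protocol 4.2.1.1 says that infusion reactions include "pyrexia, chills, rigors, dyspnoea, urticaria, bronchospasm, hypotension, and hypertension", so such a symptom during infusion can equally be read as an excepted infusion reaction. The text does not settle this, so it is a point to clarify and not a finding.

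**The effect is small.** This stands. With 6 evaluable patients, a changed verdict needs at least two DLT-level events, one of them unclassified.

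**Conclusion.** The point holds for the visible wording: a recovered grade 3-4 infusion reaction at a Cycle 1 infusion given without pre-medication meets no listed DLT criterion, and a grade 4 patient may be replaced and leave the MTD set. It is worth fixing because it sits in the rule behind the primary endpoint.

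The size is probably small: about 1 to 2 percentage points in the chance of passing the 1-in-6 rule at reaction rates of 1% to 2%, and about 7 points at the 6.1% bound. A reader might infer from much higher reaction rates that the MTD is likely to be wrong; nothing in the documents supports such rates.

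The anchor is itself weak. The 48 patients span many doses, the trial was not in Japanese patients, and their pre-medication is not stated. The 1/48 is an assumption too, since Protocol 1.4 rules out further DLTs only at that dose level and later ones. A figure in Protocol 4.1.3.2 is not visible in the text reviewed, so the conclusion covers the wording only. Confidence is medium.

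**What to change.** 1. **Protocol.** The sponsor must reconcile 4.1.3.2, 4.2.1.1 and 4.2.2.1 so that an infusion reaction at an infusion given without pre-medication has a stated DLT status. This should say whether the symptoms listed in 4.2.1.1, when recorded separately, are treated as infusion reactions. No clinical rule is proposed here.
2. **SAP 7.4.** Leave the MTD set and the governing DLT count unchanged. Beside them, show per cohort on the treated set, with expansion patients separately, the count that also includes patients with a drug-related grade 3-4 infusion reaction in Cycle 1, whether or not they were replaced. Fix the list of terms before database lock.

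The cost is wording in three protocol sections and one extra column, from data already collected. A cohort may look slightly less favourable, and the denominator may exceed 6, which needs a footnote. Protocol 2.3 records the end of development. If DLT decisions and the database are already closed, both parts should be done in the report and labelled post hoc, the first as a statement of how such reactions were classified.

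### The electrolyte DLT bullet names grade 3 only, so a refractory grade 4 event that recovers within 14 days is not a DLT as written

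*Protocol*

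**What the plan says.** Protocol 4.1.3.2 defines a DLT as a drug-related adverse event in Cycle 1 that meets one of a list of criteria. The general non-haematological criterion is "CTCAE grade 3 or 4 non-haematologic toxicity (except incompletely treated nausea", followed by further exceptions that end "skin toxicity, fatigue, infusion reaction, electrolyte, hyperglycaemia, AST, or ALT". Electrolyte events are therefore outside the general criterion at both grades.

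Specific bullets then return some of the exempted terms. Electrolyte events return as "Any electrolyte CTCAE grade 3 adverse event which is refractory to optimal correction therapy". Hyperglycaemia returns at grade 3 or higher when it is "hyperglycaemia resistant to treatment with anti-diabetic agents", and skin toxicity also returns at grade 3 or higher.

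One residual bullet applies whatever the type of toxicity. It opens "No recovery from a non-DLT CTCAE grade", covers grade 3 or higher, and asks for recovery to grade 1 or lower "within 14 days of administered dose". A closing paragraph lets the investigator and sponsor treat other events as DLTs case by case, but the grade it names is 2.

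Protocol 4.1.3.3 sets the MTD as the highest dose tested with a DLT in no more than 1 of 6 evaluable patients. SAP 5.1 repeats this rule. SAP 7.4 refers back to protocol 4.1.3.2 for the DLT definition and adds no criterion.

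**The concern.** A toxicity definition should be ordered: if an event counts at one grade, the same event at a higher grade should also count. The electrolyte bullet breaks that order for one combination of circumstances.

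The DLT count is the primary endpoint, and the limit of 1 in 6 leaves no slack, so one event classified differently can change the conclusion about a dose. DLT status also leads to the dose-reduction provisions in protocol 4.1.3.6 and to expedited reporting as an event of special interest under 5.2.2.1. The wording therefore affects more than a table.

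**Working it through.** **1. Sample-size figure.** Three cohorts of up to 6 give 6 + 6 + 6 = 18 evaluable patients, and 18 + 6 in the expansion cohort = 24. Both agree with protocol 7.6 and the synopsis. This point does not affect them.

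**2. Exempted terms set against their own bullets (protocol 4.1.3.2).**

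| Exempted term | Grade in its own bullet | Added condition |
|---|---|---|
| Infusion reaction | 2 or higher | despite pre-medication |
| Nausea, vomiting | 2 or higher | lasting 7 days or more on antiemetics |
| Skin toxicity | 3 or higher | not down to grade 2 with up to 14 days of supportive care |
| Hyperglycaemia | 3 or higher | resistant to treatment |
| Electrolyte | 3 | refractory to correction |
| Fatigue | 3 | over 96 hours, with worse ECOG status |
| Untreated diarrhoea, AST, ALT | no own bullet | residual non-recovery bullet only |

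**3. Drug-related Cycle 1 electrolyte events, classified literally.**

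- Grade 3, refractory: DLT under the electrolyte bullet.
- Grade 4, refractory, not at grade 1 or lower by 14 days: DLT under the residual bullet.
- Grade 4, refractory, back to grade 1 or lower within 14 days: no criterion applies. The general criterion exempts it, the electrolyte bullet names grade 3, the residual bullet is not met, and the discretionary paragraph names grade 2.
- Grade 3 or 4, corrected on treatment and recovered within 14 days: not a DLT at either grade, so nothing is out of order here.

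Only the third case is out of order with the first.

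**4. Timing of the residual bullet.** Fourteen days after the Day 1, 8 and 15 doses is Day 1 + 14 = 15, 8 + 14 = 22 and 15 + 14 = 29. SAP 5.1 ends the MTD evaluation period at the start of Cycle 2, or after 21 days if Cycle 2 is not started. The documents do not say whether non-recovery established after that still counts. The conclusion here does not depend on the answer, because the third case recovers in time.

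**5. Effect on the 1-of-6 rule.** Suppose one patient's event falls in the gap and is not counted.

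| Patients with a dose-limiting event | Counted | Rule met if all count | Rule met as counted |
|---|---|---|---|
| 1 of 6 | 0 of 6 | yes | yes |
| 2 of 6 | 1 of 6 | no | yes |
| 3 of 6 | 2 of 6 | no | no |

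One uncounted patient reverses the conclusion only when exactly two of six are affected.

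**The case against.** Much of the case on the other side stands.

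- **The combination is unusual.** The event must be grade 4, refractory to correction, and still back to grade 1 or lower within 14 days of the dose.
- **Prior experience is reassuring.** Protocol 1.4 reports 81 patients in the two earlier trials, with drug-related events mostly of grade 1 or 2. The one DLT was a pulmonary haemorrhage.
- **Classification is not mechanical.** Protocol 4.1.3.2 requires the investigator and sponsor to agree each DLT, and 3.1.1 gives an independent external expert a part in reviewing DLT evaluation. A refractory grade 4 event would probably be discussed. That makes an oversight less likely but does not alter the wording, and no written criterion would require the event to be counted.
- **The fatigue bullet also names grade 3 alone,** so the grade-or-higher form is not universal. Whether that leaves a similar gap depends on the CTCAE scale for fatigue, which the documents do not reproduce. It is not pressed here.

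A reader might infer that AST and ALT escape the definition altogether, since they are exempted and have no bullet of their own. The documents do not support that. The residual bullet excludes no toxicity type, so a grade 3 or higher AST or ALT rise that has not recovered by 14 days is a DLT. Protocol 4.1.3.2 also says that short-lived laboratory changes are to be taken into account in defining a DLT, so leaving out transient rises appears deliberate. Asking for a separate criterion for every exempted term would be a preference, not the correction of an error.

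**Conclusion.** The inconsistency is real and narrow. It rests on a literal reading of protocol 4.1.3.2: a refractory grade 4 electrolyte event that recovers in time is not a DLT, while a refractory grade 3 event is. The contrast with the skin and hyperglycaemia bullets suggests a drafting slip, though the documents do not state the intent.

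No magnitude is claimed. A reader might be tempted to assume a true DLT rate and a share of missed events and to work out how much more easily a dose would pass. The documents supply neither figure, and such a result would only return its own assumptions. What can be said is that one uncounted patient changes the MTD conclusion when two of six are affected. The point deserves attention because it sits in the definition behind the primary endpoint, not because the case is likely to be common.

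**What to change.** The sponsor and investigator should reconcile the electrolyte bullet in protocol 4.1.3.2 with the exception list above it and the neighbouring bullets, so that a higher grade is not left outside a criterion that a lower grade meets. If the present wording is intended, the protocol should say so and give the reason. The clinical threshold is theirs to set.

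Protocol 2.3 records that treatment was recommended to stop and that oncology development has ended, so the practical step is in reporting. The clinical trial report, or a revision or addendum if it is already written, should state whether any Cycle 1 grade 4 electrolyte event occurred and how it was classified for the MTD. If there was none, one sentence closes the matter.

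The cost is a change of wording and a check of the Cycle 1 electrolyte events. Sample size and procedures do not change. The DLT count would change only if such an event occurred and was reclassified.
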